## 4 STUDY DESIGN

### 4.1 Study Overview

This is a prospective, multicenter, observational study designed to collect gastrointestinal related data in patients with CF.

Eligible subjects will be consented and enrolled in the study at the Enrollment Visit. At the visit, the subject or parent/guardian will complete the PROs using their mobile device (e.g., smartphone or tablet). The PROs will consist of four questionnaires: Patient Assessment of Constipation-Symptoms (PAC-SYM), Patient Assessment of Gastrointestinal-Symptoms (PAGI-SYM), Patient Assessment of Constipation Quality of Life (PAC-QOL) and the disease-specific questionnaire. The disease-specific questionnaire will include the Bristol Stool Scale and will collect information on presence of fecal incontinence, stool quality and frequency. At the Enrollment Visit, weight and height will be collected in addition to medical history and concomitant medication information. The subject or parent/guardian will complete the PROs outside-the-clinic setting per the Schedule of Events using their mobile device.

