### 15.4 Analysis of Secondary Endpoints

Constipation is defined as <3 bowel movements in the past week and/or Bristol Stool type 1 or 2. The secondary endpoint upon which the sample size is based is the number (%) of enrolled subjects with any occurrence of constipation during 1 month of follow-up (the period prevalence). Treatment for GI symptoms and constipation will be summarized based on the percentage of enrolled subjects receiving and initiating treatment at time of enrollment visit. To evaluate whether CF subjects are adequately treated, the number and percentage of subjects with GI symptoms and constipation on treatment will be reported. All GI related treatments will be classified by medication type/class.

Individual GI symptoms will be extracted from the PAC-SYM and PAGI-SYM questionnaires. For each GI symptom, frequency and severity will be summarized at each assessment as follows: number (%) of subjects with GI symptom, severity of GI symptom (mean score and distribution of severity score) and change in severity scores from the enrollment visit by whether subjects were receiving treatment.

Mean overall (and by sub-scale) PRO scores for PAC-SYM, PAGI-SYM and PAC-QOL at scheduled assessments will be reported including evaluation of within and between subject variability. Group comparisons of mean scores by subjects receiving/not receiving treatment and by those with/without constipation will also be made. Absolute change in PRO scores from enrollment visit to scheduled assessments will be reported based on subjects receiving/not receiving treatment for constipation. To examine these effects, figures displaying mean PRO scores by scheduled assessment will be created. Additionally, mixed effects models for repeated measures will be fit with PRO scores as the outcome and covariates for visit, treatment, pancreatic status, age group and the interaction between treatment and visit.

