2.1 Data Flow

An electronic data capture system, Medidata Rave, was utilized for collection of study data. Study personnel at each site entered data from a participant's visit onto the protocol-specific Case Report Form (eCRF). Study participants were not be identified by name in the study database or on any data capture screens, however, they were identifiable by a unique participant identification number. Only study personnel at the individual sites were able to link the study ID to the participant's name. The Medidata Rave eCOA/ePRO system, a regulatory compliant system which allows participants in a study using Medidata Rave EDC to complete and submit forms and data for patient-reported outcomes electronically on a mobile device to the Medidata Rave EDC System, was also utilized. Study personnel at each site registered study participants using their unique identification number which generated an activation code unique to that participant. Study site personnel provided the participant with their activation code. The study participant downloaded the Medidata Rave eCOA/ePRO app to their mobile device and used their unique activation code to create their ePRO login and password.

The following schedule of events shows the schedule and data collected at the baseline visit and outside-of-clinic follow-up.

	BASELINE VISIT (DAY 1)	DAY 7 (+ 1 day)	DAY 14 (+ 1 day)	DAY 28 (+ 1 day)
Informed Consent	X			
Review Eligibility	X			
CFF Registry ID, CF Diagnosis, and Demographics	X			
Medical History/GI History	X			
Concomitant Medication Review	X			
Height	X			
Weight	X			
Assist with downloading mobile application for completing questionnaires	X			
Complete PAC-SYM, PAGI-SYM, and disease-specific questionnaires on mobile device	X	X	X	X
Complete PAC-QOL	X			X

After data was entered into the study database, data validation checks were applied on a regular basis. Queries were entered, tracked, and resolved through the system directly. The study database was updated in accordance with the resolved queries. All changes to the study database were documented in an audit trail.

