[1] Unknown status of constipation at each week is defined as either incomplete Disease-Specific Questionnaire or failure to answer question 2 on the Disease-Specific Questionnaire.

[2] To summarize all follow-up weeks, constipation status implies that a participant had at least one or more week where they met the self-defined definition of constipation.

Exhibit 6.4.x Model-Based Summary of Clearance of Constipation among Participants Who Had Constipation at Baseline Visit.

This exhibit reports statistical results for the clearance of constipation among participants who had constipation at baseline visit and had at least one follow-up Disease-Specific Questionnaire fully completed. Weekly clearance of constipation (1=yes, 0=no) is the outcome of interest in a generalized linear mixed model (GLMM) with either logit link (for odds ratio interpretation) or log link (for relative risk interpretation), participant-specific random effects, and adjustments for baseline constipation treatment, age group, sex, and week. In formula:

Weekly Clearance of Constipation (0/1) ~ Baseline Constipation Treatment + Age Group + Sex + Week + Participant-Specific Random Effect

Note: Constipation treatment at baseline was determined based on ATC coding of concomitant medications.

Exhibit 6.4.1 for Protocol-Defined Constipation

Exhibit 6.4.2 for Self-Defined Constipation

Exhibit 6.5.x Model-Based Summary of Emergence of Constipation among Participants Who Had No Constipation at Baseline Visit.

This exhibit reports statistical results for the emergence of constipation among participants who had no constipation at baseline visit and had at least one follow-up Disease-Specific Questionnaire fully completed. Weekly emergence of constipation (1=yes, 0=no) is the outcome of interest in a generalized linear mixed model (GLMM) with either logit link (for odds ratio interpretation) or log link (for relative risk interpretation), participant-specific random effects, and adjustments for baseline constipation treatment, age group, sex, and week. In formula:

Weekly Emergence of Constipation (0/1) ~ Baseline Constipation Treatment + Age Group + Sex + Week + Participant-Specific Random Effect

Note: Constipation treatment at baseline was determined based on ATC coding of concomitant medications.

Exhibit 6.5.1 for Protocol-Defined Constipation

Exhibit 6.5.2 for Self-Defined Constipation

A.7 Summary of Current Management of GI Symptoms

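### The clearance and emergence models (SAP Exhibits 6.4.x and 6.5.x) adjust for no severity within baseline-constipation strata, so treatment can look harmful through confounding by indication

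*SAP*

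**What the plan says.** Protocol 4.1 describes the design: "This is a prospective, multicenter, observational study designed to collect gastrointestinal related data in patients with CF". Treatment is whatever each participant is taking or starting in routine care. For these exhibits, "Constipation treatment at baseline was determined based on ATC coding of concomitant medications".

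Exhibits 6.4.x concern "Clearance of Constipation among Participants Who Had Constipation at Baseline Visit", and Exhibits 6.5.x the complementary group. Both use a generalized linear mixed model with a logit or log link, participant random effects and "adjustments for baseline constipation treatment, age group, sex, and week". The formulas are written out in full:

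- Clearance: "Weekly Clearance of Constipation (0/1) ~ Baseline Constipation Treatment + Age Group + Sex + Week + Participant-Specific Random Effect"
- Emergence: "Weekly Emergence of Constipation (0/1) ~ Baseline Constipation Treatment + Age Group + Sex + Week + Participant-Specific Random Effect"

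Each is run for protocol-defined constipation (6.4.1, 6.5.1) and for self-defined constipation (6.4.2, 6.5.2).

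A severity measure is available. The schedule in SAP 2.1 has the row "Complete PAC-SYM, PAGI-SYM, and disease-specific questionnaires on mobile device", marked at baseline and at all three follow-up weeks. Neither document plans a propensity score, a severity-adjusted sensitivity model or a caution about causal reading for these exhibits.

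**The concern.** Among participants constipated at baseline, those on treatment are plausibly the more chronically affected, while some of the untreated simply had one bad week. Constipation status is a past-week state, so a single poor week is enough to enter the clearance model. The untreated would then clear more often whatever treatment does. Among those not constipated at baseline, the treated are plausibly the people more prone to constipation, so it would emerge more often in them.

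Age group, sex and week do not capture this. The participant random effect does not either, because the model takes it to be independent of treatment. At stake is the direction of a treatment odds ratio or relative risk in a study whose third secondary objective is to inform later treatment algorithms.

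**Working it through.** **The plan's own figure.** The documents state no power, effect size or sample size for these models. The only sizing figure is 400 participants (Protocol 15.7). It reproduces: 1.96² × 0.25 × 0.75 / 0.045² = 355.7, so 356 evaluable; 356/0.88 gives 405 and 356 × 1.12 gives 399, both close to 400.

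**Size of the two sets (assumed).**

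- Using the protocol's 25% and 12% loss: clearance 400 × 0.25 × 0.88 = 88; emergence 400 × 0.75 × 0.88 = 264.
- The 25% is a one-month period prevalence, so 88 is an upper-end figure for constipation at baseline alone. With an assumed weekly prevalence of 13–16%, 400 gives 52–64 constipated at baseline, or 46–56 after 12% loss.
- The clearance set is therefore roughly 50–90 participants.

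**Simulation A: the SAP's logit model with no treatment effect.** Random intercept, three follow-up weeks, age group, sex and week, with a true treatment odds ratio of 1. Baseline severity drives both treatment and outcome with the same odds ratio per SD. Assumed: typical weekly clearance about 50% and emergence about 15%; 50% and 35% treated; random-intercept SD 1. Odds ratios come from 20,000 simulated participants. False-harm rates come from 250 trials of 88 or 264 participants (nominal 2.5%).

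| Severity OR per SD | Clearance OR as planned | False significant harm | Emergence OR as planned | False significant harm |
|---|---|---|---|---|
| 1 | 1.02 | 2.4% | 0.96 | 2.4% |
| 1.5 | 0.84 | 4.8% | 1.13 | 8.0% |
| 2 | 0.63 | 22.8% | 1.46 | 43.2% |
| 3 | 0.38 | 63.6% | 2.56 | 93.6% |

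Below 1 looks harmful for clearance, above 1 for emergence. The first row shows simulation noise of a few hundredths, so the second decimal carries little weight.

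With severity added:

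- Measured without error: the odds ratio returns to 0.97–1.02 (clearance) and 0.96–0.99 (emergence), and two-sided rejection at trial size is 3–8%.
- Measured with reliability 0.7 (assumed): at 2 per SD it is 0.89 and 1.14; at 3 per SD, 0.72 and 1.39. At 2 per SD the false clearance log odds ratio falls from ln 0.63 = −0.46 to ln 0.89 = −0.12, so about a quarter remains.

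**Simulation B: baseline PAC-SYM as an imperfect marker of chronic tendency, no treatment effect.** Assumed: weekly prevalence near 15%, about 37% treated, treatment log-odds rising 0.5–1.0 per SD of chronic tendency, and PAC-SYM correlated 0.80–0.89 with that tendency. The clearance odds ratio moves from 0.51–0.68 as planned to 0.72–0.83 with PAC-SYM added. Emergence moves from 1.7–2.7 to 1.2–1.5. With about 53 participants constipated at baseline, the standard error of the treatment log odds ratio is 0.42 in both models, so the extra term costs almost no precision.

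**Simulation C: as B, but treatment truly works and is already acting at baseline.**

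| Strength of indication | Clearance, true OR about 2.7: planned → with PAC-SYM | Emergence, true OR 0.33: planned → with PAC-SYM |
|---|---|---|
| Weaker | 1.13 → 1.06 | 0.87 → 0.95 |
| Stronger | 0.82 → 0.91 | 1.30 → 1.12 |

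Adjustment pulls the estimate towards 1. With weaker indication that is slightly further from the truth; with stronger indication it is slightly nearer. Neither model recovers the benefit.

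**The case against.** **Treatment is only an adjustment here.** The SAP lists it among the adjustments in 6.4 and 6.5, whereas Exhibits 5.6.1 and 7.4 name a predictor of interest. Clearance and emergence match no numbered endpoint, and the study is mostly descriptive. This limits the importance of the point but does not remove it. The preceding Exhibits 6.3.1 and 6.3.2 cross-tabulate constipation by treatment, and Appendix A.8 makes repeating 6.3–6.5 for other symptoms depend on having symptom-specific treatment data. That condition makes sense only if treatment is the exposure. The plan also chooses its link for odds-ratio or relative-risk interpretation.

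**Adjustment is a weak cure.** This stands in part. Baseline PAC-SYM in established users is measured on treatment, and Simulation C shows that it can hide a benefit. Under the null, the residual odds ratios still point towards harm. It is a reason to show both models rather than replace one.

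**Stronger readings the documents do not support.**

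- A reader might infer that baseline stool frequency and Bristol type go unused. They define protocol-defined constipation, and so set the strata for 6.4.1 and 6.5.1; only their finer grading within a stratum is lost.
- A reader might infer that pancreatic status was dropped from these models. The protocol's list, "covariates for visit, treatment, pancreatic status, age group and the interaction between treatment and visit", belongs to a model of PRO scores, whose SAP counterpart is Exhibit 7.4. The protocol has no clearance or emergence model, and its PRO-score list has no baseline-severity term either.
- A reader might infer that the direction will be wrong, or that adjustment would put it right. The documents give no strength of indication, and the simulations show only partial correction.

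**Conclusion.** The point holds as a limited one that should be addressed. Both formulas lack any severity term beyond restriction on yes/no baseline status, treatment is not randomised, and a collected baseline score could reduce the resulting bias.

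The bias is small if severity acts with an odds ratio of about 1.5 per SD on both paths, and large enough to produce frequent false signals of harm from about 2. These strengths, the clearance and emergence rates, the treated fractions and the PAC-SYM correlation are all assumptions. Only the logit link was simulated. With no true effect, adjustment reduces the bias; with a benefit already acting at baseline it may not.

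These are supportive exhibits with no stated power. The primary feasibility endpoint and the period-prevalence endpoint do not depend on them.

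**What to change.** In Exhibits 6.4.x and 6.5.x, keep the planned model and report beside it a second one with the same terms plus the baseline PAC-SYM total score as a continuous covariate. State in both exhibits that the treatment estimate is an association, and that the adjusted one is conditional on current severity, which for established users already reflects treatment. Where the two models differ, say that the result depends on severity.

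Do not add stool frequency, Bristol category and pancreatic status by default. The clearance set is small (about 50–90, assumed), the first two already define the strata for protocol-defined constipation, and the larger model was not examined here.

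Costs: one covariate already in the database and one more column per exhibit. Participants without a complete baseline PAC-SYM drop out of the second model; there may be some, because SAP 2.3 requires only one fully completed questionnaire at baseline. The adjustment removes only part of the bias and can mask a real benefit, so it does not license a causal conclusion.

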#### **Describe current management of GI symptoms:**

- Evaluate treatment for GI symptoms and constipation at time of enrollment visit:
  15. Number (%) of all subjects receiving treatment
  16. Number (%) of all subjects initiating treatment
  17. Number (%) of all subjects receiving treatment by Medication class/type
  18. Among subjects with GI symptoms and constipation, number (%) receiving treatment
- Evaluate symptom scores due to treatment:
  19. Mean PRO scores (also mean differences and 95% confidence interval) comparing subjects receiving treatment for GI symptoms to those not receiving treatment
  20. Among subjects receiving treatment for constipation, mean absolute change in PRO scores over time overall and by medication type/class

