Descriptive statistics will be used to summarize the total and domain scores by protocol-defined constipation. Longitudinal summaries will be provided, using mixed-effect models with participant-specific random intercepts, as well as fixed effects for weekly protocol-defined constipation status, visit, and age group. The predictor of interest is the protocol-defined constipation status. The corresponding analyses are outlined in Appendix A, Section A.5.

Evaluation of alternative CF-specific definitions of constipation:

14. Examine alternative definitions of constipation that are CF specific based on correlation with PRO questionnaires and maximizing the area under the receiver operating characteristic (ROC) curve for PAC-SYM scores
15. Number (%) reporting constipation based on patient self-assessment. Examine concordance of self-reported constipation against protocol/alternate definitions using Cohen's kappa coefficient

The corresponding analyses are outlined in Appendix A, Section A.6.

3.4.3 Current management of GI symptoms:

16. Number (%) of all participants receiving treatment at baseline
17. Number (%) of all participants initiating treatment at baseline
18. Number (%) of all participants receiving treatment by medication class/type
19. Among participants with GI symptoms and constipation, number (%) receiving treatment
20. Change in distribution of GI symptoms and stool frequency/type by GI treatment at baseline
21. Mean PRO scores (also mean differences and 95% confidence interval) by GI treatment at baseline
22. Among participants receiving or initiating treatment for constipation, mean absolute change in PRO scores over time overall and by medication type/class

The corresponding analyses are outlined in Appendix A, Section A.7.

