Exhibit 7.1 Summary of Treatment for GI Symptoms and Constipation at Baseline

This table summarizes the number of participants initiating treatment, receiving treatment (along with the medication type/class), or neither at baseline.

	Age Category		All Enrolled Participants (N=n)
	Age < 18 (N=n)	Age ≥ 18 (N=n)	
Neither Initiating nor Receiving Treatment	n (%)		
Initiating or Receiving GI Treatment			
Type of Treatment			
Non-Constipation			
Medication 1			
...			
Medication m			
Constipation			
Medication 1			
...			
Medication m			
Route			
GI Tube			
Others			
Note: missing data			

Note: See Appendix D for a list of GI medications of interest. GI/Constipation medications were derived from all concomitant medications based on ATC coding.

Exhibit 7.2 Summary of GI Symptoms and Constipation by Receiving Constipation Treatment

This table summarizes GI symptoms and constipation status at baseline by receiving constipation treatment.

	Receiving Constipation Treatment	
	Yes (N = n)	No (N = n)
GI Symptoms	Symptom 1 (n = x) Symptom 2 (n = x) ... Symptom s (n = x) Any Symptom (n = x)	
Protocol-Defined Constipation	Yes (n = x)	
Self-Defined Constipation	Yes (n = x)	
Other Definition of Constipation	Definition 1 (n = x) Definition 2 (n = x) ... Definition d (n = x)	

Note: missing data

Note: See Appendix B for a list of prespecified alternative definition of constipation.

Exhibit 7.3.x.y Change in [GI Symptom X] from Baseline among [Subgroups Defined by Constipation Treatment at Baseline]

This table is similar to the 5.4.x tables for each subgroup defined by constipation treatment at baseline (initiating/receiving or neither). The table shows the change in distribution for each symptom X (including stool frequency/type) from baseline at each follow-up week.

		Week 1 (N =) [1] (Mean Score = , 95% CI =)						Week 2 (N =) [2] (Mean Score = , 95% CI =)						Week 4 (N =) [3] (Mean Score = , 95% CI =)					
Baseline (Mean = , 95% CI =)	n (%) Worse	Absent	Mild	Moderate	Severe	Very Severe		Absent	Mild	Moderate	Severe	Very Severe		Absent	Mild	Moderate	Severe	Very Severe	
		Absent	n (%)	n (%)				n (%)	n (%)					n (%)	n (%)				
		Mild	n (%)					n (%)						n (%)					
		Moderate						n (%)						n (%)					
		Severe						n (%)						n (%)					
		Very Severe						n (%)						n (%)					
		n (%) Improved					n (%) No Change	n (%) Improved					n (%) No Change	n (%) Improved					n (%) No Change

[1] Consider participants with both baseline and Week 1 data

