[2] Consider participants with both baseline and Week 2 data

[3] Consider participants with both baseline and Week 4 data

Exhibit 7.3 Changes in GI Symptoms from Baseline by Constipation Treatment

[figure not shown]
The following table shows the changes in GI symptoms from baseline at each follow-up week in subgroups defined by constipation treatment, i.e. not treated versus treated (initiating or receiving). This is a collapsed version with less details compared to the 7.3.x exhibits.

GI Symptom	Baseline Mean (95% CI)	Week 1					Week 2					Week 4				
		N [1]	Mean (95% CI)	Worsen – n (%)	No Change – n (%)	Improved – n (%)	N [1]	Mean (95% CI)	Worsen – n (%)	No Change – n (%)	Improved – n (%)	N [1]	Mean (95% CI)	Worsen – n (%)	No Change – n (%)	Improved – n (%)
Symptom 1	Not Treated	Mean (95% CI)	n	mean (CI)	n (%)	n (%)	n (%)	n	mean (CI)	n (%)	n (%)	n (%)	n	mean (CI)	n (%)	n (%)
	Treated	Mean (95% CI)	n	mean (CI)	n (%)	n (%)	n (%)	n	mean (CI)	n (%)	n (%)	n (%)	n	mean (CI)	n (%)	n (%)
Symptom 2	Not Treated															
	Treated															
...																
Symptom s	Not Treated															
	Treated															

[1] N per each follow-up week is defined as the number of participants who had data at both baseline and the follow-up week.

Exhibit 7.4 Longitudinal Summary of PAC-SYM, PAGI-SYM, and PAC-QOL Total and Domain Scores by Constipation Treatment

This table provides longitudinal summaries of the total and domain scores, for all participants and subgroups stratified protocol-defined constipation. The estimates are obtained from mixed-effect models with participant-specific random intercept, as well as fixed effects for indicator of constipation treatment, week, and age group. The predictor of interest is the indicator of constipation treatment.

A.8 Additional Exhibits for Consideration Given Data Availability and Feasibility

Exhibit: PAC-SYM, PAGI-SYM, and PAC-QOL total/domain scores by modulator use and types

Exhibits: Selected analysis on completion of ePROs, total/domain scores of PAC-SYM, PAGI-SYM, and PAC-QOL, summary of disease-specific questionnaire by 3 age groups: <12, ≥12 and <18, and ≥18 (Note: for participants <12 years old, parents or guardians would complete the ePROs)

Exhibits: Selected analysis by age groups corresponding to PROMISE for future comparison (less than 6, 6-11, 12+)

Exhibits: Repeat Exhibits 6.3-6.5 for specific symptoms of interest, e.g. nausea or bloating

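### The SAP lists starting treatment at baseline as its own count, but Exhibit 7.1 gives it no row, and Exhibits 7.3.x.y and 7.3 and item 22 pool starters with established users, so pooled change cannot be read as change after starting treatment

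*SAP*

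**What the plan says.** **Endpoint lists.** Protocol section 5.2 has receiving treatment as endpoint 15 and, separately, endpoint 16: "Number (%) of all subjects initiating treatment". Protocol section 15.4 says the summary will be based on the "percentage of enrolled subjects receiving and initiating treatment at time of enrollment visit". SAP section 3.4.3 keeps the separation; item 16 is receiving and item 17 is "Number (%) of all participants initiating treatment at baseline".

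**Exhibit 7.1.** The introductory sentence keeps three groups: "This table summarizes the number of participants initiating treatment, receiving treatment (along with the medication type/class), or neither at baseline". The shell below it has a row for participants doing neither and one combined row, "Initiating or Receiving GI Treatment", under which the medication types are listed. It has no row for starters alone.

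**Change from baseline.** The Exhibit 7.3.x.y tables are built for "each subgroup defined by constipation treatment at baseline (initiating/receiving or neither"), and the collapsed Exhibit 7.3 contrasts "not treated versus treated (initiating or receiving"). SAP item 22 reads: "Among participants receiving or initiating treatment for constipation, mean absolute change in PRO scores over time overall and by medication type/class". The matching protocol endpoint (20) covers only those receiving treatment for constipation, so the SAP has widened the population. Exhibit 7.4 uses one treatment indicator with week and age group, and no interaction.

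**Source of treatment status.** The notes to Exhibits 6.4.x, 6.5.x and 7.1 say that treatment is derived from concomitant medications by ATC coding. Neither document states how a participant who is starting treatment is told apart from one already on it.

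**The concern.** There are two consequences, of different kinds.

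The first is about reporting. The SAP preface says that the document gives detailed specifications for all its tables. A programmer who builds Exhibit 7.1 from the shell will produce the union of starters and established users, and item 17 cannot be recovered from a union.

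The second is about interpretation. The questionnaires ask about the last week (Exhibits 5.1.1 and 5.3.1). For someone who starts treatment at the enrollment visit, the baseline answers appear to describe a week before that treatment. For an established user they describe a week on treatment. A change from baseline pooled over both has no single meaning. This matters because one protocol objective is to inform later treatment algorithms, and the protocol groups these endpoints under symptom scores due to treatment. A reader will be inclined to take the treated group's change as a signal about treatment.

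**Working it through.** **Step 1: trace each count to a cell.**

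| Quantity | Listed in | Cell in the Exhibit 7.1 shell |
|---|---|---|
| Receiving | Protocol endpoint 15; SAP item 16 | only within the merged row |
| Initiating | Protocol endpoint 16; SAP item 17 | only within the merged row |
| Neither | Exhibit 7.1 text | own row |

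The rest of Appendix A.7 does not fill the gap. Exhibit 7.2 splits by receiving constipation treatment, yes or no, without saying where starters go. Exhibits 7.3.x.y and 7.3 pool, and Exhibit 7.4 has a single indicator.

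**Step 2: what the pooled change measures.** Let f be the share of starters in the treated group, C_new their mean improvement from baseline, and C_est that of established users. Then

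pooled change = f × C_new + (1 − f) × C_est

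C_new − pooled change = (1 − f) × (C_new − C_est)

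The pooled value understates the starters' change when they improve more than established users, and equals it only if the two groups change alike (or f = 1). If C_est = 0, the pooled value is exactly f × C_new.

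**Step 3: illustration for item 22, PAC-SYM score.** Protocol section 1.2 gives about 0.5 points as minimal and about 1 point as moderate improvement, for the general adult population. The documents give neither f nor a change by time on treatment. The values of f (5% to 50%) and of C_est (0 or 0.1) are assumptions.

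| f | C_new 0.5, C_est 0 | C_new 0.5, C_est 0.1 | C_new 1.0, C_est 0 |
|---|---|---|---|
| 5% | 0.025 | 0.12 | 0.05 |
| 10% | 0.05 | 0.14 | 0.10 |
| 20% | 0.10 | 0.18 | 0.20 |
| 30% | 0.15 | 0.22 | 0.30 |
| 50% | 0.25 | 0.30 | 0.50 |

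Example for f = 20%: 0.2 × 0.5 + 0.8 × 0 = 0.10, and with C_est = 0.1, 0.2 × 0.5 + 0.8 × 0.1 = 0.18. Reported separately, starters would show 0.5 in both cases.

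These figures do not carry over to Exhibit 7.3, which reports single symptom items and stool frequency and type. The same mixing occurs there, but the PAC-SYM benchmark does not apply to those items.

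**Step 4: Exhibit 7.4.** With treatment, week and age group as fixed effects and no interaction, the treatment coefficient is the same at baseline and at every follow-up. It is a difference in level, not in change. A three-level treatment variable would give two level differences and still no estimate of change after starting. Protocol section 15.4 specifies the treatment-by-visit interaction that would supply it.

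**Step 5: sample size.** No stated figure depends on this point. The sample size rests on constipation prevalence: 1.96² × 0.25 × 0.75 / 0.045² = 355.7, rounded up to 356, and 356 / 0.88 = 404.5, or 405, against a stated figure of about 400. Treatment groups do not enter.

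**The case against.** **The endpoint has not been dropped.** A reader might infer from the shell that the initiating count will not be reported. The documents do not support that: item 17 is listed and the Exhibit 7.1 text promises it. This objection stands. What remains is a conflict between the list and text on one side and the table layout on the other.

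**The plan sets no endpoint for change after starting treatment.** Item 22 openly defines a pooled population, the protocol allows the SAP to modify the analysis, and the parent objective is descriptive. This is fair, and it means that the pooled analysis does not fail a stated target. It does not make the pooled result interpretable, and the SAP gives no reason for widening protocol endpoint 20.

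**The size is unknown.** A reader might infer that the treated group's change would be close to zero even if starting treatment helps. That needs a small share of starters and stable established users. The documents give no share, and the protocol synopsis expects overall disease fluctuation. Nor is initiating defined, so even the pre-treatment status of a starter's baseline is an inference. This objection stands; the table under the working is an illustration only.

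**Exhibit 7.3 reports more than a mean.** It also gives numbers worsened, unchanged and improved, and Exhibits 7.3.x.y give full cross-tabulations. True, but all of these are computed on the pooled group, so they mix the same two baselines.

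**The data may not support a split.** ATC coding identifies drug class, not recency. Medications are reviewed only on Day 1, and neither document says that start dates are recorded. This is a real constraint, but item 17 already requires starters to be identified.

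**Conclusion.** The point holds in a limited form. From the text alone, without assumptions: items 16 and 17 are separate counts, the Exhibit 7.1 shell gives only their union, no other exhibit in Appendix A.7 shows starters alone, and no rule defines initiating. Also from the text: Exhibits 7.3.x.y and 7.3 and item 22 pool starters with established users, so their change from baseline should not be read as change after starting treatment or as stability on treatment.

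Conditionally: if starters improve more than established users, the pooled value understates the starters' change by (1 − f) times the difference between the groups. For a 0.5-point PAC-SYM improvement with stable established users, the pooled value is 0.025 to 0.25 across assumed shares of 5% to 50%. The actual size cannot be found from the documents.

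This is a minor point about reporting and interpretation of descriptive secondary endpoints. The primary endpoint is unaffected.

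**What to change.** 1. State in the SAP how initiating at the enrollment visit is derived from the recorded medication information, including how to classify someone already on one agent who starts another.
2. Split the merged row of Exhibit 7.1 into participants starting at the enrollment visit and participants already receiving treatment. Say in Exhibit 7.2 where starters are counted.
3. Report Exhibits 7.3.x.y and 7.3 and item 22 by initiating, already receiving and neither, with the count in each group. Keep the pooled treated group as a supplementary row.
4. If the three-level variable is used in Exhibit 7.4, include the treatment-by-visit interaction from protocol section 15.4.

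The cost is one derived variable and some extra rows. The initiating group may be small, with wide intervals. The split also depends on the collected medication data identifying new starts. If they cannot, the SAP should say so, since item 17 could then not be reported either, and should label the pooled change results accordingly.
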